## 6 STUDY OBJECTIVES

### 6.1 Primary Objective(s)

[figure not shown]
**Table 6–1 Primary Objective**

Objective(s)	Endpoint(s)
Performance:  To obtain device-specific performance clinical data	Performance:  Percent of ‘yes’ responses to the question of: Did UNITY VCS using anterior segment surgical functionality perform per the intended use as defined in Protocol Section 5.1?

### 6.2 Secondary Objective(s)

**Table 6–2 Secondary Objective(s)**

Objective(s)	Endpoint(s)
Performance:  To obtain device-specific performance clinical data	Performance:  Time from incision entry to incision closure

### 6.4 Safety Objective(s)

**Table 6–3 Safety Objective(s)**

[figure not shown]
Objective(s)	Endpoint(s)
To obtain device-specific safety clinical data	Adverse events (ocular and nonocular; serious and nonserious) Device deficiencies Secondary surgical interventions Unplanned intraoperative surgical procedures

## 7 INVESTIGATIONAL PLAN

### 7.1 Study Design

This is a prospective, interventional, open-label, single-arm, nonrandomized and multicenter clinical study in the United States of America (USA) and/or Australia with approximately a 1-month follow-up.

**Figure 7-1** Study Design Flow Chart

## 7.2 Rationale for Study Design

The UNITY VCS is a Class II nonimplantable medical device in the USA and a Class IIb nonimplantable medical device in the EU and AUS. For this class category, there are no currently well-established study designs governed by health authorities or international standards. The prospective design of this traditional feasibility study will reduce sources of bias and confounding variables. The intended patient population represents the majority of patients that will require use of the investigational device for cataract removal surgery where inclusion/exclusion criteria were carefully selected to reduce confounding variables.

The study design was also carefully thought out to allow it to represent a real world setting to ensure minimal intervention to the site's standard of care; this ensures the study gains the most realistic response with regard to device performance and safety. [REDACTED]

[REDACTED]

[REDACTED]

A potential weakness of the current study design is the fact that it is a single-arm study. However, this single-arm design is justified given that there are well established data regarding safety and performance of cataract surgery. As such, the safety and performance results from this study can be compared against this rich body of evidence to ensure the device meets state of the art standards.

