## 7.4 Rationale for Choice of Comparator Product

There is no comparator in this study.

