## 8 STUDY POPULATION

The study population will consist of male and female subjects (over the age of 18 years) with a diagnosis of age-related noncomplicated cataract (unilaterally). It is aimed to enroll (consent) approximately 120 subjects in up to 5 sites in the United States and/or Australia with a target of 100 subjects treated, with 10 to 40 subjects per site. Site-specific targets may vary based upon individual site capabilities and each site may include more than one surgeon. Each surgeon will perform at least 10 surgeries, but no more than 33% of the total subjects treated. Estimated time needed to recruit subjects for the study is approximately 5 months; however, unanticipated circumstances may shorten or lengthen this time and would not require amendment of this protocol. Because a 10% screening failure rate is expected and 10% for lost to follow-up, approximately 120 subjects are expected to be enrolled to ensure 100 completed subjects.

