### 12.6.1.2 Analysis Methods

For all safety measures, descriptive statistics will be presented based on the type. For categorical variables, summary statistics will include sample size (subjects/eyes), number in category, and percentage in each category. For continuous variables, number of subjects/eyes, mean, median, standard deviation, minimum, and maximum will be reported. Individual subject data listings will also be provided.

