### **5.3.1 Adverse Events**

All adverse events reported to Alcon will be accounted for in the reporting. Descriptive summaries (counts and percentages) and listings will be presented. The applicable definition of an adverse event is in the study protocol. A listing of all adverse events will be constructed to provide further details.

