### **5.3.3 Secondary Surgical Interventions**

Descriptive statistics (numbers and percentages) of eyes with secondary surgical interventions (SSI) will be presented. In addition, a listing of subjects with SSIs will be produced.

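### Safety percentages have no planned confidence intervals, although the protocol rests its single-arm design on being able to compare them with published evidence

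*Protocol*

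**What the plan says.** Protocol 7.2 concedes that having a single arm may be a weakness. It justifies the design by the established data on cataract surgery, against which the results "can be compared against this rich body of evidence to ensure the device meets state of the art standards". Section 7.4 confirms that "There is no comparator in this study". The safety objective in Table 6–3 is "To obtain device-specific safety clinical data", and neither document has a safety hypothesis (Protocol 12.6.1.1, SAP 5.2).

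The statistics planned for safety are:

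- Protocol 12.6.1.2: "For categorical variables, summary statistics will include sample size (subjects/eyes), number in category, and percentage in each category".
- SAP 5.3.1, adverse events: "Descriptive summaries (counts and percentages) and listings will be presented".
- SAP 5.3.2, device deficiencies: counts by category and a listing, with no percentage.
- SAP 5.3.3: "Descriptive statistics (numbers and percentages) of eyes with secondary surgical interventions (SSI) will be presented".
- SAP 5.3.4, unplanned intraoperative procedures: descriptive statistics, not specified further, and a listing.

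The performance endpoints are treated differently. SAP 4.3.1 gives the primary percentage a two-sided exact binomial 95% interval. SAP 4.3.2 gives 95% intervals for the mean and the median surgery time. The sample size (Protocol 12.8, SAP 6) is justified only by the interval half-width for the primary percentage. Protocol section 8 plans up to 5 sites "with a target of 100 subjects treated", from about 120 enrolled.

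**The concern.** The protocol names one use for the safety results beyond description: setting them beside outside evidence. A percentage from about 100 eyes cannot be set beside an external rate without some statement of its precision. This matters most for uncommon surgical complications, where the likely observation is zero, one or two events. A table showing 0% looks better than most non-zero published rates, yet it may say little about whether the true rate is lower.

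The plan already treats precision as its own criterion. It sizes the study on an interval half-width and reports intervals for both performance endpoints, but does not do so for safety, although safety data are a stated objective and the study is meant to support marketability in Europe.

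**Working it through.** **Inputs**

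- Treated eyes: about 100, one eye per subject (Protocol section 3 and section 8).
- Safety denominator: all eyes with attempted use of the device (Protocol 12.2.2, SAP 2.2). It could exceed 100. Assuming 120 enrolled less 10% screen failure gives 120 × 0.9 = 108. The most it could be, with all 120 enrolled subjects treated, is 120.
- Interval method: exact binomial (Clopper-Pearson), two-sided 95%, as SAP 4.3.1 uses for the primary endpoint.
- True safety event rates: the readable text gives none, so any used below are assumptions.

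**Step 1. The plan's own precision figure.** At p = 0.5 and n = 100 the half-width is 1.96 × √(0.5 × 0.5 / 100) = 1.96 × 0.05 = 9.8%. This agrees with the stated figure of below 10%. It concerns the performance question only.

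**Step 2. The same kind of check for safety.** For x events in n eyes, the lower limit is the 2.5% quantile of Beta(x, n − x + 1), or 0 if x = 0. The upper limit is the 97.5% quantile of Beta(x + 1, n − x). For x = 0 the upper limit reduces to 1 − 0.025^(1/n), so with n = 100 it is 1 − 0.025^0.01 = 3.62%.

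| Events | Percentage at n = 100 | Exact 95% interval, n = 100 | Upper limit, n = 108 (assumed) | Upper limit, n = 120 (maximum) |
|---|---|---|---|---|
| 0 | 0% | 0 to 3.62% | 3.36% | 3.03% |
| 1 | 1% | 0.03 to 5.45% | 5.05% | 4.56% |
| 2 | 2% | 0.24 to 7.04% | 6.53% | 5.89% |
| 5 | 5% | 1.64 to 11.28% | 10.47% | 9.46% |

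(The limit for 1 of 100 is 5.446%, which is 5.4% to one decimal.)

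**Step 3. How often zero would be seen.** The chance of no event in 100 eyes is (1 − p)^100:

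| Assumed true rate p | Chance of no event in 100 eyes |
|---|---|
| 0.5% | 60.6% |
| 1% | 36.6% |
| 2% | 13.3% |
| 3% | 4.8% |

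A complication with a true rate of 1% would be missed entirely in more than a third of such studies, and the planned table would then show 0 and 0%.

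**Step 4. Could an interval be implied?** SAP 5.3.1 and 5.3.3 name counts or numbers and percentages. SAP 5.3.4 says only descriptive statistics. For categorical variables, Protocol 12.6.1.2 defines these as sample size, number and percentage. None of these sections names an interval, and none carries a redaction mark.

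**The case against.** The strongest reply is that this is a traditional feasibility study with no hypotheses, whose safety objective is to obtain data. Counts, percentages and listings meet that objective. Section 7.2 says that results can be compared, not that they will be, and no analysis section specifies a comparison, a benchmark or a pass rule. Because numerators and denominators are reported for adverse events and SSIs, and each subject contributes one eye, a reader can derive the intervals.

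Much of this stands. A reader might infer that the plan commits to a formal comparison and then fails to support it, or that outside comparison is the only way to any conclusion. The documents support neither reading: the wording is permissive and the descriptive objective can be met without a comparison. Nor does the omission bias an estimate or lose data. That few events would be misread is an inference about readers, not something the plan says.

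Two further limits apply. Part of section 7.2 is redacted, so a benchmark may exist there; if it does, the interval is more useful, not less. The protocol's lists of statistics are also not strictly exhaustive: Protocol 12.4.1.2 lists no interval for categorical summaries, yet SAP 4.3.1 adds one for the primary endpoint. That shows the SAP can add an interval where it is wanted. It has not done so for safety.

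The descriptive label does not answer the point. SAP 4.2 calls the effectiveness analyses descriptive only, and SAP 4.3 still attaches intervals to them. An interval is a description of precision, not a test.

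**Conclusion.** The point holds as a mismatch between a stated use and the planned reporting. The protocol relies on the safety results being comparable with outside evidence, and no safety percentage comes with an interval. At 100 eyes, 0, 1 and 2 events leave upper limits of 3.6%, 5.4% and 7.0%. Across the plausible range of 100 to 120 treated eyes, the upper limit for zero events falls only from 3.6% to 3.0%, so the conclusion does not depend on the exact denominator.

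The limits assume independent eyes with a common event rate. The probabilities in Step 3 rest on assumed true rates.

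The absence of safety hypotheses is not an error in this design, and the plan does not claim that few events would prove state-of-the-art safety. Device deficiencies are to be reported as counts only, so no percentage there lacks an interval. The change should be made because it is specific, nearly free and limits what an observed 0% can be taken to show.

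**What to change.** In Protocol 12.6.1.2 and SAP 5.3.1, 5.3.3 and 5.3.4, add a two-sided exact binomial 95% confidence interval, by the SAP 4.3.1 method and on the safety analysis set, to the percentage of eyes with:

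- any ocular adverse event
- any ocular serious adverse event
- any device-related adverse event
- any secondary surgical intervention
- any unplanned intraoperative surgical procedure

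State that any comparison with published rates will cite these intervals. The 18 individually listed serious event terms in Protocol 11.1 may stay as counts and percentages, since an interval for each would mostly repeat the same zero-event limit. Device deficiencies may stay as counts.

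The cost is some wording, a few lines of programming and a few extra table columns. No data or subjects are added, and the study stays descriptive. The downside for the sponsor is that wide intervals will make the safety result look less favourable than a bare percentage.

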### 7.2.1 Purpose and Timing of Interim Analyses and Resulting Design Adaptations

Not applicable. There are currently no planned interim analyses.

## 7.3 Rationale for Duration of Treatment/Follow-Up

The follow-up schedule was designed to allow collection of data at key time points that yield relevant performance and safety outcomes. The follow-up period will allow for adequate safety monitoring of adverse events; if patients develop complications, those will typically be present within approximately 1 month of cataract surgery.

## 7.4 Rationale for Choice of Comparator Product

There is no comparator in this study.

## 7.5 Data Monitoring Committee

Not applicable

## 8 STUDY POPULATION

The study population will consist of male and female subjects (over the age of 18 years) with a diagnosis of age-related noncomplicated cataract (unilaterally). It is aimed to enroll (consent) approximately 120 subjects in up to 5 sites in the United States and/or Australia with a target of 100 subjects treated, with 10 to 40 subjects per site. Site-specific targets may vary based upon individual site capabilities and each site may include more than one surgeon. Each surgeon will perform at least 10 surgeries, but no more than 33% of the total subjects treated. Estimated time needed to recruit subjects for the study is approximately 5 months; however, unanticipated circumstances may shorten or lengthen this time and would not require amendment of this protocol. Because a 10% screening failure rate is expected and 10% for lost to follow-up, approximately 120 subjects are expected to be enrolled to ensure 100 completed subjects.

### 8.1 Inclusion Criteria

Written informed consent must be obtained before any study specific assessment is performed. Upon signing informed consent, the subject is considered enrolled in the study.

Subjects eligible for inclusion in this study must fulfill **all** of the following criteria:

1. Subject must be able to understand and sign an IRB/IEC approved Informed Consent form.
2. Willing and able to attend all scheduled study visits as required per protocol.
3. Adults (>18 years of age) with a clinically documented diagnosis of age-related noncomplicated cataract
4. Eligible to undergo primary hydrophobic acrylic intraocular lens implantation into the capsular bag.
5. Subject has clear intraocular media (including clear corneas) other than the cataract in the operative eye
6. Keratometry: 41 to 46 D, anterior chamber depth: 2.5 to 4 mm and axial length: 22 to 25 mm

## 8.2 Exclusion Criteria

Subjects fulfilling **any** of the following criteria are not eligible for participation in this study.

1. Women of childbearing potential, defined as all women who are physiologically capable of becoming pregnant and who are not postmenopausal for at least 1 year or are less than 6 weeks since sterilization, are excluded from participation if any of the following apply:
  - a. they are currently pregnant,
  - b. have a positive urine pregnancy test result at Screening,
  - c. intend to become pregnant during the study period,
  - d. are breastfeeding.

Subjects who become pregnant during the study will not be discontinued; however, data will be excluded from the effectiveness analyses because pregnancy can alter refraction and visual acuity results.

2. Laser assisted fragmentation in the operative eye.
3. Planned postoperative procedures during the course of the study (e.g., corneal refractive surgery) in the operative eye.
4. More than 1+ guttata in the operative eye.
5. A history of chronic or recurrent inflammatory eye disease or trauma (e.g., iritis, scleritis, uveitis, iridocyclitis, rubeosis iridis, herpes simplex keratitis) in the operative eye.
6. Previous intraocular or corneal surgery in the operative eye.
7. Any ocular comorbidity (other than cataract) that may confound the results (e.g., zonular instability or zonular dehiscence or pseudoexfoliation, ocular surface disease, synechiae, iris atrophy, shallow anterior chamber, lens subluxation) in the operative eye.
8. Diagnosis of glaucoma or ocular hypertension (IOP > 21 mmHg) in the operative eye.

9. Any topical or systemic medications known to interfere with visual performance or complicate cataract surgery.
10. Diagnosed with severe systemic (e.g., history of cerebral vascular accident) or retinal disorders (e.g., macular degeneration, diabetic retinopathy, or other retinal pathology that might limit postoperative visual acuity or predispose the subject to postoperative retinal complications) in the operative eye.
11. A poorly dilating pupil or other pupil defect that prevents the iris from retracting peripherally to at least 6 mm diameter dilation in the operative eye.
12. Mechanical or surgical manipulation required to enlarge the pupil at time of surgery.
13. Conditions that, per investigator's clinical judgment, would confound the results of this investigation.
14. Currently participating in another drug or device clinical trial or having participated in another drug or device clinical trial within 30 days of enrolment into this study.

### **8.3 Rescreening of Subjects**

Rescreening of subjects is not allowed in this study.

If subjects initially met all inclusion/exclusion criteria but surgery cannot be completed within 60 days of initial screening, then the investigator per their SOC should verify that subject continues to meet all inclusion/exclusion criteria at the time of surgery.

## **9 TREATMENTS ADMINISTERED**

### **9.1 Investigational Product(s)**

*Test Product(s):* UNITY Vitreoretinal Cataract System (VCS)

*Comparator Product(s) (If applicable):* Not applicable

**Table 9–1**

**Test Product**

Test Product	UNITY VCS (including the console, remote control, foot controller, UNITY Cataract FMS Pack, and UNITY Anterior Vitrectomy Kit)*
--------------	---

Manufacturer	Alcon Laboratories, Inc. [name]
Indication for use and intended purpose in the study	
Intended Use: The UNITY VCS, consisting of the console and compatible devices, is intended to facilitate management of fluid and gases, as well as removal, grasping, cutting, illumination and coagulation of ocular materials.
 
Indications For Use: The UNITY VCS, consisting of the console and compatible devices, is indicated for use during anterior and posterior segment ophthalmic surgery.
 
While the UNITY VCS is able to perform anterior and posterior segment functionalities, only the anterior segment functionalities will be enabled during this study. All posterior segment functionalities will be disabled in this study.

Product description and parameters available for this study	
The UNITY VCS in this study is a surgical instrument for use in anterior segment ophthalmic surgeries. The product's capabilities include driving a variety of handpieces that provide the ability to emulsify and remove the crystalline lens, cut and remove vitreous as well as coagulation to stop bleeding.
 
While UNITY VCS is able to perform anterior and posterior segment functionalities, only the anterior segment functionalities will be enabled during this study. All posterior segment functionalities will be disabled in this study.

Formulation	N/A
Usage	The UNITY VCS anterior segment functionalities will be used as directed in the user manual.

Packaging description	Each UNITY VCS console and all compatible anterior segment devices will be packaged individually and have an investigational product specific serial or lot number [REDACTED] [REDACTED] [REDACTED] [REDACTED]
Labeling description	Investigational labeling regulations apply for UNITY VCS console, remote control, foot controller, UNITY Cataract FMS Pack and UNITY Anterior Vitrectomy Kit. These devices will be labeled appropriately (e.g., “CAUTION – Investigational device. Limited by Federal [or United States] law to investigational use” or “Exclusively for Clinical Investigation” or “For Clinical Trial Use Only”). Each unit will be identifiable via a serial or lot number.
Training and/or experience requirements for device	The UNITY VCS should only be used by authorized study personnel. It should only be operated according to the operating instructions as listed in the associated user manual and DFUs. [REDACTED]
Storage conditions	Temperature and relative humidity listed below apply to room environmental conditions preceding and during device use.  Temperature: 50 to 95 °F (10 to 35 °C) Operating; 14 to 131 °F (-10 to 35 °C) Nonoperating  Relative Humidity: 10 to 95% without condensation  See User Manual for complete requirements and instructions.
Additional information	Not applicable
Supply	UNITY VCS which includes the console and all compatible anterior segment devices will be shipped to the site by the sponsor.  Refer to the MOP for a detailed description.

More information on the test product be found in the Investigator's Brochure and Directions for Use for the UNITY VCS.

### **9.3 Treatment Assignment / Randomization**

Only after signing the ICF will a subject be assigned a subject number by the electronic data capture system.

All subjects who meet the inclusion/exclusion criteria and sign informed consent will undergo cataract surgery with the UNITY VCS. Bias will be minimized as this is a single-arm study.

If both eyes qualify for the study, the study eye will be determined per investigator's discretion.

There will be no randomization of subjects.

### **9.4 Treatment masking**

Not applicable as this is an open-label, single-arm study.

### **9.5 Accountability Procedures**

Upon receipt of IP, the investigator or delegate must conduct an inventory of equipment and accessories by serial or lot number, complete study-specific confirmation of receipt

procedures as described in the MOP, and retain any required documentation in the investigator's clinical study records.

- All IPs sent to the investigator must be accounted for by study sponsor personnel, and in no case be used in an unauthorized manner.
- Refer to Section 11 of this protocol for additional information on the reporting of device deficiencies and to the MOP for information on return of investigational products associated with these events.

The investigator is responsible for allowing de-installation of the provided UNITY VCS and to return (or destroy) all unused sponsor-provided accessories and supplies as directed at the conclusion of the study or according to the instructions provided in the MOP.

## **9.6 Changes to concomitant medications, treatments/ procedures**

After the subject is enrolled into the study, the investigator must instruct the subject to notify the study site about:

- Any new medications
- Alterations in dose or dose schedules for current medications,
- Any medical procedure or hospitalization that occurred or is planned
- Any nondrug therapies (including physical therapy and blood transfusions).

The investigator must document this information in the subject's case history source documents.

